4.7. Allocation concealment and blinding

Participants will be given a sealed envelope with the letter of the study group name in it and will be allowed to present it to the OR. Anesthesia providers involved in patient management will be allowed to know the drugs given and groups due to differences in anesthesia techniques, ethical issues, and patient diversity. Apart from patient management, the anesthetist will not be involved in any other study processes. Only participants assigned to groups will not know which group they will be selected for.

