4.2. Study design

A multi-centered, randomized, controlled, single-blinded trial will be conducted at Dilla University General and Teaching Hospital and Hawassa University Comprehensive and Specialized Hospital.

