4.6. Random sequence generation

The eligible participants presenting for gynecologic surgery at both study areas during the study period will be selected. Participants will be allocated to study groups by a computer-generated random allocation sequence number created by an independent anesthetist with a 1:1 allocation to the treatment group (T) and control group (C) the night before surgery.

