4.10. Data collection procedures

After getting ethical clearance from the Dilla University College of Health Sciences and Medicine ethical review board, a structured questionnaire will be formed and translated into the respective languages by the principal investigator (PI). Two BSC anesthetists involved in patient management will be selected at both study areas and trained in the overall process of participant handling and data collection.

During the preoperative period

Patients undergoing gynecologic operations during the study period will be assessed and told about the study process and anesthetic the day before the surgery. The patient will receive maintenance fluid, had bilateral peripheral IV lines secured, and was NPO the night before surgery. On the morning of the procedure, both a standard informed consent form for the procedure and a separate consent form for the study will be checked and available.

The availability and functionality of the bilateral IV line, and NPO status will be checked, and prophylactic drugs will be given. Standard preoperative questionnaires will be used, and data will be collected through patient responses and medical records, such as patient monitoring and charts.

At intraoperative period

Routine ASA monitoring will be checked and applied for patients in both groups when the patient presented to the OR. The functionality and availability of the bilateral IV line and urinary catheter will be rechecked. Propofol (3 mg/kg) will be given to induce anesthesia after the patient had been pre-oxygenated for both groups. An intravenous bolus of 0.5 mg/kg of ketamine during the induction phase for patients in the treatment group, then a continuous infusion of 0.2 mg/kg/hr. Of ketamine. A bolus of 1.5 mg/kg will be given before induction, and the same dose of lidocaine will be administered every 15 to 20 minutes after induction of anesthesia until the start of skin closure.

Patients in the control group will be induced with fentanyl 2 μ g/kg given during induction of anesthesia with propofol 3mg/kg. 0.5 μ g /kg of fentanyl will be given every 20-30 minutes up to the start of skin closure.

Intubation will be performed after administering 1.5–2 mg/kg IV suxamethonium. Inhalational anesthetics as availabilities (Isoflurane 0.75–2% and Halothane 1%_ 2%) were opened after the position of the ETT was confirmed, and Dexamethasone 0.15mg/kg IV bolus will be given after securing the ETT.

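### The participant, the only blinded party, carries the sealed envelope with her group letter to the OR, which needlessly puts at risk the blinding of a self-reported primary outcome

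*Combined protocol and SAP*

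**What the plan says.** Section 4.2 sets the design: "A multi-centered, randomized, controlled, single-blinded trial will be conducted". Section 4.6 describes a "computer-generated random allocation sequence number created by an independent anesthetist", with "1:1 allocation to the treatment group (T) and control group (C) the night before surgery".

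Section 4.7 then describes the route of the assignment: "Participants will be given a sealed envelope with the letter of the study group name in it", and the participants "will be allowed to present it to the OR". On who is blinded it says two things: "Anesthesia providers involved in patient management will be allowed to know the drugs given and groups", and "Only participants assigned to groups will not know which group they will be selected for". It also says that the treating anesthetist takes no other part in the study.

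The primary outcome in section 4.8.1.1 is postoperative pain severity. Section 4.10 measures it by VAS at PACU discharge and at 6, 12 and 24 hours, and section 4.9 defines the VAS as patient-reported. On study consent, section 4.10 says that on the morning of surgery "a separate consent form for the study will be checked and available".

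The envelope is described as sealed. The plan does not say whether it is opaque or numbered, who prepares it, hands it over and opens it, when it is handed over, or what is done if it arrives opened.

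**The concern.** The plan places the assignment in the hands of the only party it intends to blind, before anesthesia starts. The letters are the initials of treatment and control, so they are not a neutral code.

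Pain on a VAS is open to expectation: a participant who believes she received the new technique, or was denied it, may score differently for that reason alone. Analgesic requests and nausea, both secondary, also depend on what the participant says. A systematic difference in reporting between arms would be added to the treatment difference, and no analysis in section 4.12 could separate the two.

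There is a lesser risk to the integrity of allocation. If the group becomes known between allocation and the OR, it could affect whether that participant goes ahead, is deferred, or is moved to the other arm.

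**Working it through.** The plan states no figure on this point, so the check is mainly one of setting sections side by side.

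1. **Who is blinded?** Participants only (4.7). Providers know drugs and groups. No blinding of outcome assessors or analysts is described.
2. **Who holds the code before the OR?** The participant (4.7).
3. **What does the code show?** The letter of the group, T or C (4.6 and the Executive Summary).
4. **Does the outcome depend on the blinded party?** Yes (4.8.1.1, 4.9 and 4.10).
5. **Is there an operational reason for this route?** None is given. The person who needs the assignment is the treating anesthetist in the OR, who is already unblinded.
6. **Is there an interval in which an opened envelope could matter?** Allocation is the night before surgery (4.6), and the study consent form is checked the next morning (4.10). The handover time is not stated, but it must precede arrival in the OR.

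Items 1 to 4 establish the risk to blinding, and item 5 makes it needless. Item 6 supports the secondary risk, less firmly, because the handover time is missing.

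**What a reporting bias would do, if there were one.** The inputs are the SD of 1.9 and the 31 or 35 per group (4.5 and the Executive Summary). The average between-arm reporting bias *b*, in VAS cm, is an assumption. With no true effect, at one time point and two-sided 5%:

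- SE = 1.9 × √(2/n), which is 0.483 at n = 31 and 0.454 at n = 35.
- Rejection probability = Φ(b/SE − 1.96) + Φ(−b/SE − 1.96).
- Example, n = 35 and b = 0.5: b/SE = 1.101, so Φ(−0.859) + Φ(−3.061) = 0.195 + 0.001 = 0.196.

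| Assumed b (cm) | 31 per group | 35 per group |
|---|---|---|
| 0 | 0.050 | 0.050 |
| 0.25 | 0.081 | 0.085 |
| 0.5 | 0.179 | 0.196 |
| 0.75 | 0.343 | 0.379 |
| 1.0 | 0.545 | 0.596 |

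Here *b* is averaged over all participants: the fraction who learn their group times the between-arm shift among them. With an assumed shift of 1.0 cm (0.5 cm in opposite directions in the two arms), 10% to 40% unblinded gives b = 0.1 to 0.4 cm. The last rows would need far more unblinding or a larger shift.

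Section 4.5 also writes 1.9 under the symbol for a variance. If it is a variance, the SD is √1.9 = 1.38, the SE at n = 35 falls to 0.33, and every entry for b above zero rises. The table shows sensitivity to a bias; it does not estimate one.

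**The case against.** The envelope is sealed, and section 4.7 says that participants will not know their group. Nothing permits a participant to open it. The harm needs a broken seal and an understanding of the letter, and the documents do not say that participants are told what T and C mean. Study materials are translated into local languages, so an English initial may not explain itself. All of this stands: what the text shows is a risk, not a breach.

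A reader might infer that allocation concealment fails. The documents do not support that. Concealment protects against those who enrol foreseeing an assignment. The sequence is computer-generated by an independent anesthetist, and one participant's envelope reveals nothing about the next. The morning consent check may only verify a form signed earlier; the time of signing is not stated. Tampering by ward staff would be conjecture, since no section mentions them handling envelopes. What remains is the narrower risk of withdrawal, deferral or reassignment after an envelope has been opened.

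A reader might also call participant blinding the only protection the plan offers. Section 4.7 adds another, that the treating anesthetist has no other study role. Section 4.10 weakens it by training anesthetists involved in patient management to collect data. That contradiction needs its own resolution, and moving the envelope does not settle it.

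**Conclusion.** The point holds as a needless risk to participant blinding, with a secondary risk of selective withdrawal, deferral or reassignment. It rests on the procedure written in section 4.7 and on a self-reported primary outcome, and it needs no assumed number. It should be corrected, but it does not show that the trial's results would be biased.

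The size is unknown. A reader might be tempted to express it as a share of the planned effect: 20% unblinded with a 1.0 cm between-arm shift gives 0.20 cm, and 0.20 / (0.5 × 1.9) = 0.20 / 0.95 = 21%. The documents do not support that percentage. The 20% and the 1.0 cm are invented inputs. The 0.95 cm takes medium as 0.5 SD, which does not match 31 per group: that number implies √(2/31) × (1.96 + 0.84) = 0.71 SD, or 1.35 cm at SD 1.9, which would give about 15%. If 1.9 is a variance, both denominators change again. No percentage should be quoted.

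**What to change.** Do not route the envelope through the participant. Rewrite sections 4.6 and 4.7 along these lines:

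- The independent anesthetist who makes the sequence prepares sequentially numbered, opaque, sealed envelopes, with a separate run of numbers for each hospital.
- The envelopes are stored securely in the OR area of each hospital.
- Once eligibility and signed study consent are confirmed, the treating anesthetist opens the next number in the OR area, out of the patient's sight. This matters because she is still awake: both regimens start at or before induction.
- The envelope number and the time of opening are logged against the participant. Any envelope found opened or used out of order is recorded.
- Section 4.6 is reworded so that the sequence exists in advance but a participant's group is revealed only at opening, not the night before.

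The cost is wording, envelopes and a log sheet. The treating anesthetist is already unblinded, so no blinding is given up, and sample size, outcomes and treatments are unchanged. There are two small downsides. Study drugs can be prepared only after opening. Each hospital also needs secure storage handled by its existing staff, because a single independent anesthetist cannot hold envelopes at two hospitals.

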4.8. Study variables

4.8.1. Dependent (outcome) variables

4.8.1.1. Primary outcome variable

- The postoperative pain severity

4.8.1.2. Secondary outcome variables

- Postoperative analgesic requests between groups
- The occurrence of postoperative nausea and vomiting (PONV) between the groups
- The occurrence of intraoperative cardiac adverse events between groups

4.8.2. Independent variables

- Age
- Height
- Weight
- ASA physical status
- BMI
- Educational background
- Marital status
- Anesthetic experience
- Type of diagnosis and procedure
- Participants' hemoglobin and hematocrit
- Preoperative hemodynamic variables

4.9. Operational definitions

Nausea: The experience associated with the pressure to vomit

Opioid-free analgesia: A combination of various opioid-sparing techniques with absolute avoidance of opioids for pain relief in the pre-and postoperative periods.

Opioid-free anesthesia: It is a combination of various opioid-sparing techniques with absolute avoidance of opioids from induction of anesthesia until the extubation time

Postoperative nausea and vomiting: Any nausea, retching, or vomiting occurring in the first 24 hours after surgery

The Postoperative pain: pain felt up to 24 hours after an operation by the patient's expression

NRS: Valid and reliable tool for assessing pain intensity in all populations, regardless of literacy level([1](#), [50](#)). It employs a 0-to-10 rating scale, with zero representing no pain and 10 representing the worst possible pain.

VAS: This is a pain rating scale; the scores are derived from patient-reported valuations of symptoms that are recorded at 1 point along a 10 cm line that shows a continuum between the 2 edges of the scale, which are "no pain" and "worst pain([51](#))

Vomiting: Projection of contents of the stomach out through the mouth.

4.10. Data collection procedures

After getting ethical clearance from the Dilla University College of Health Sciences and Medicine ethical review board, a structured questionnaire will be formed and translated into the respective languages by the principal investigator (PI). Two BSC anesthetists involved in patient management will be selected at both study areas and trained in the overall process of participant handling and data collection.

During the preoperative period

Patients undergoing gynecologic operations during the study period will be assessed and told about the study process and anesthetic the day before the surgery. The patient will receive maintenance fluid, had bilateral peripheral IV lines secured, and was NPO the night before surgery. On the morning of the procedure, both a standard informed consent form for the procedure and a separate consent form for the study will be checked and available.

The availability and functionality of the bilateral IV line, and NPO status will be checked, and prophylactic drugs will be given. Standard preoperative questionnaires will be used, and data will be collected through patient responses and medical records, such as patient monitoring and charts.

At intraoperative period

Routine ASA monitoring will be checked and applied for patients in both groups when the patient presented to the OR. The functionality and availability of the bilateral IV line and urinary catheter will be rechecked. Propofol (3 mg/kg) will be given to induce anesthesia after the patient had been pre-oxygenated for both groups. An intravenous bolus of 0.5 mg/kg of ketamine during the induction phase for patients in the treatment group, then a continuous infusion of 0.2 mg/kg/hr. Of ketamine. A bolus of 1.5 mg/kg will be given before induction, and the same dose of lidocaine will be administered every 15 to 20 minutes after induction of anesthesia until the start of skin closure.

Patients in the control group will be induced with fentanyl 2 μ g/kg given during induction of anesthesia with propofol 3mg/kg. 0.5 μ g /kg of fentanyl will be given every 20-30 minutes up to the start of skin closure.

Intubation will be performed after administering 1.5–2 mg/kg IV suxamethonium. Inhalational anesthetics as availabilities (Isoflurane 0.75–2% and Halothane 1%_ 2%) were opened after the position of the ETT was confirmed, and Dexamethasone 0.15mg/kg IV bolus will be given after securing the ETT.

Anesthesia will be maintained with inhalational agents according to the patient's tidal volume of 6–8 ml/kg adjusted to maintain oxygen saturation >95% with 3- 4 ml 100% oxygen flow, and end-tidal CO₂ between 32 and 45 mmHg. Muscle relaxation will be maintained with vecuronium 0.8 mg/kg. Intraoperative anesthesia depth will be assessed by clinical signs as well as by patient monitoring. Estimated intraoperative blood loss will be supplied with ringer lactate or normal saline.

The intraoperative participants' data will be collected from the anesthesia record chart and patient monitoring. Intraoperative hemodynamic variables will be collected every 10 minutes. Intraoperative cardiac adverse events such as intraoperative bradycardia (pulse rate less than 50 bpm), tachycardia (PR greater than 100 bpm), hypertension, and hypotension we diagnosed and managed as per institutional protocol. Intraoperative nausea or vomiting in both groups will also be managed as an institutional protocol.

When the surgeon begins skin closure, the inhalational agent will be turned off. A pre-prepared reversal agent bolus (neostigmine 0.05 mg/kg with atropine 0.02 mg/kg IV) was administered for patients given long-acting muscle relaxants after checking the adequacy of spontaneous ventilation, adequate movement of the respiratory bag, oxygen saturation >95percentage and ETCO₂ between 32 and 45 mmHg after the skin is closed.

During the postoperative period

The postoperative pain severity will be assessed by the validated VAS starting from the patient's discharge from PACU to 24 hours postoperatively. Data will be collected at discharge from PACU, at 6 hours, 12 hours, and 24 hours postoperatively. Analgesia request at postoperative times will be recorded as the patient's request for analgesia according to the VAS score. PONV data will be collected from the time of arrival at PACU at 6 hours, 12 hours, and 24 hours postoperatively according to the patient's signs and symptoms.

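### Sections 4.7 and 4.10 conflict on whether unblinded treating anesthetists collect data; no visible section names who records the postoperative outcomes, and 4.7 read literally lets that person know the group

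*Combined protocol and SAP*

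**What the plan says.** Section 4.7 (Allocation concealment and blinding) makes three statements:

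- On knowledge of the group: "Anesthesia providers involved in patient management will be allowed to know the drugs given and groups".
- On the treating anesthetist's role: "Apart from patient management, the anesthetist will not be involved in any other study processes".
- On who is blinded: "Only participants assigned to groups will not know which group they will be selected for".

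Section 4.10 (Data collection procedures) opens by saying that two "anesthetists involved in patient management will be selected at both study areas and trained in the overall process of participant handling and data collection". For the intraoperative period it says that "data will be collected from the anesthesia record chart and patient monitoring". The postoperative records are then described without naming anyone who makes them:

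- VAS: "Data will be collected at discharge from PACU, at 6 hours, 12 hours, and 24 hours postoperatively".
- Analgesia requests: recorded as the patient's "request for analgesia according to the VAS score".
- PONV: "PONV data will be collected from the time of arrival at PACU at 6 hours, 12 hours, and 24 hours postoperatively", on the basis of what the patient shows and reports.

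Section 4.11 refers to data collectors who are trained the week before collection starts, and to the principal investigator picking up completed forms each day. The budget table in 4.15 pays for three data collectors and one supervisor. Neither section says whether the collectors are the anesthetists of 4.10, or whether they know the allocation. Section 4.16 (Annex One) appears only as a heading, and the questionnaire is not shown.

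**The concern.** The exclusion in 4.7 is the plan's own safeguard. The treating anesthetists know which drugs were given, so the plan keeps them away from the rest of the study. Section 4.10 describes staff in the same terms and trains them to collect data. A site that follows 4.10 as written could have the unblinded anesthetist record the outcomes without breaking any sentence of that section.

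What is at stake is detection bias. A recorder who knows the group may prompt, interpret or count differently in the two arms. In an open-label comparison of anesthetic techniques this is one of the few sources of bias that staffing alone can reduce.

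**Working it through.** No formula applies to the conflict itself, so the check is a comparison of the text. The only arithmetic is a count of the records affected.

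**1. Are the same people meant?** Both 4.7 and 4.10 identify the staff by their involvement in patient management. Under 4.7 they know the group and do nothing else in the study. Under 4.10 they are trained in data collection. As worded, the two cannot both hold.

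**2. Does 4.10 limit the data collection to the intraoperative chart?** It might be meant that way. But the training covers the whole process, and the sentence introduces a section that runs through the preoperative, intraoperative and postoperative periods. The text states no limit.

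**3. Do the data collectors of 4.11 and 4.15 settle it?** The budget has 3 collectors. Section 4.10 has two anesthetists, which means 2 in total or 2 × 2 = 4 if two per site. Three matches neither. This hints at a separate role but does not establish one, and nothing is said about whether the collectors know the allocation.

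**4. May the recorder know the group?** Section 4.7 says that only participants are kept unaware. Taken literally, anyone else may know, including whoever records outcomes. This is an inference from a general sentence; no sentence addresses outcome recorders directly.

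**5. Is there another route to the allocation?** Intraoperative data are taken from the anesthesia chart, which is assumed here to list the drugs given. No visible sentence keeps the person who reads that chart apart from the person who later records VAS, requests and PONV.

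**6. How exposed is each outcome?**

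- VAS: section 4.9 defines it as the patient's own rating, and the patient is meant to be blinded. Exposure is limited.
- Nausea: section 4.9 defines it as something the patient experiences, so it too comes mainly from the blinded patient. Exposure is limited.
- Retching and vomiting, which count as PONV in 4.9: the recorder may have to judge signs. Exposure is somewhat greater.
- Analgesia requests: the request is the patient's, but someone decides what counts as one and how it relates to the VAS score. Exposure is limited for the request and somewhat greater for that decision.

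**7. How many records have no named recorder?** Inputs are 70 participants (4.5) and the time points in 4.10.

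- VAS at PACU discharge, 6, 12 and 24 h: 70 × 4 = 280.
- PONV at 6, 12 and 24 h: 70 × 3 = 210. If arrival at PACU is a separate time point, which the wording leaves open: 70 × 4 = 280.
- Outcomes: the primary and two of the three secondary outcomes in 4.8.1. The third, intraoperative cardiac events, is charted during anesthesia and is outside this point.

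These are counts of scheduled records. They do not measure bias.

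**The case against.** The strongest reply has four parts.

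*The plan already answers the blinding question.* It declares itself single-blinded (4.2), and 4.7 says only participants are unaware. On that reading an unblinded recorder is permitted, and objecting to it is objecting to single-blinding. This stands in part: single-blinding is openly declared and is no fault, and the literal reading of 4.7 is the plainest one. It does not explain why 4.7 bars the treating anesthetist from other study work while 4.10 trains that person for it.

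*Training is not assignment.* The anesthetists deliver the intervention and keep the chart, so they need training anyway, and separate collectors are budgeted. This stands as a possible reading. A reader might infer from 4.10 that unblinded anesthetists are assigned to record the postoperative outcomes. No sentence says so, which is why the risk is conditional.

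*The outcomes come from a blinded patient.* This stands for VAS, for nausea and for the request itself. A reader might infer that the secondary outcomes are wide open to the recorder's influence while VAS is protected. The definitions in 4.9 do not support so sharp a contrast.

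*The recorder may be named on pages not shown.* The questionnaire and Annex One are not available, so one can say only that no visible section names the recorder. An annex could supply the name; by itself it would not reconcile 4.7 with 4.10, both of which are visible.

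**Conclusion.** The point holds in a limited form. Sections 4.7 and 4.10 contradict each other on the role of the treating anesthetists, no visible section says who records the postoperative outcomes, and 4.7 taken literally lets that person know the group. The gap covers the primary outcome and two of three secondary outcomes in all 70 participants.

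The risk of detection bias depends on who in fact records. The documents give no basis for its size or direction, and none is claimed. It is limited for VAS, nausea and analgesia requests, and somewhat greater where the recorder judges PONV signs or decides what counts as a request.

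Two stronger conclusions are tempting and unsupported. One is that the pain comparison is biased: the score is the blinded patient's own, and no text puts an unblinded person in charge of it. The other is that the trial report could not say who recorded the outcomes: the investigators will know who filled in the forms and can report it whatever the protocol says.

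The conclusion assumes that the anesthesia chart shows the drugs given and that the unseen annex does not already separate the roles. The correction is worth making because it restores the plan's own safeguard at low cost.

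**What to change.** 1. Reconcile 4.7 and 4.10 so that treating anesthetists are limited to patient management and routine completion of the anesthesia chart. They should not be asked to extract study data from it, since that is a study process of the kind 4.7 rules out for them.
2. State in 4.10 and 4.11 that VAS at PACU discharge, 6, 12 and 24 h, analgesia requests and PONV are recorded by the data collectors already in the budget. A collector must not have attended that patient's anesthetic, and must not see the allocation or the anesthesia chart until the 24 h form is closed.
3. Take intraoperative data from the chart only after that form is closed.
4. If Annex One or the questionnaire already names the recorder, cite it in 4.10.
5. If this separation is not possible with existing staff, state in the protocol and in the report that outcome recording was not blinded.

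The cost is wording and scheduling. Assessments, time points and sample size do not change. The practical difficulty is cover: three collectors are budgeted for two sites, and the plan does not say how they are divided. If each works at one site only, at least one site has no more than one collector for every visit up to 24 h. The investigators need to confirm that this is feasible.

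### The treatment arm's pre-induction study-drug bolus has no counterpart in the control arm, so it can reveal allocation to the only blinded party, who also scores the primary outcome

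*Combined protocol and SAP*

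**What the plan says.** Section 4.10 (intraoperative period) sets out the anesthetic sequence. Propofol is common to both arms and "will be given to induce anesthesia after the patient had been pre-oxygenated for both groups". For the treatment arm the section first lists ketamine: "An intravenous bolus of 0.5 mg/kg of ketamine during the induction phase for patients in the treatment group", followed by a continuous ketamine infusion. It then says: "A bolus of 1.5 mg/kg will be given before induction, and the same dose of lidocaine will be administered every 15 to 20 minutes", continuing until skin closure begins. For the control arm, the first study drug is fentanyl, "given during induction of anesthesia with propofol 3mg/kg". No study drug is listed for that arm before induction, and no infusion.

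Section 4.7 describes the blind. Anesthesia providers know the group: "Anesthesia providers involved in patient management will be allowed to know the drugs given and groups due to differences in anesthesia techniques". The blind covers one party: "Only participants assigned to groups will not know which group they will be selected for". On preparation, section 4.10 says that patients "will be assessed and told about the study process and anesthetic the day before the surgery".

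Section 4.9 defines the VAS as a patient-reported score on a 10 cm line. Section 4.10 has it recorded at PACU discharge and at 6, 12 and 24 hours. The supplied text describes no placebo, saline or dummy injection, no other masking step in the operating room, and no check on whether the blind held.

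**The concern.** The blind on the participant is the only one the plan states, and the participant supplies the primary outcome. Two secondary outcomes also depend on her: analgesic requests are hers to make, and nausea is defined as an experience. If she works out her group, nothing else in the stated blinding protects these measurements.

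The order of drugs gives her an opportunity to do so. One arm has a study-drug bolus before induction and the other does not. Anyone who knows how the two techniques differ could read her allocation from that step. Correcting the handling of the sealed envelope in section 4.7 would leave this difference in place. If beliefs about allocation influence VAS scores, the comparison between arms would carry a reporting bias that the planned t-tests and ANOVA cannot separate from a drug effect.

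**Working it through.** The plan gives no figure for this point, so there is none to reproduce. The check is mainly one of reading, followed by a calculation for scale.

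**Sequence by arm (section 4.10)**

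| Step | Treatment | Control |
|---|---|---|
| Preoperative | Bilateral IV lines, maintenance fluid, unspecified prophylactic drugs | Same |
| Before induction | Study-drug bolus, 1.5 mg/kg | No study drug listed |
| Induction | Ketamine bolus, propofol | Fentanyl, propofol |
| After the induction bolus | Ketamine infusion, repeated lidocaine | Repeated fentanyl |

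Two readings need support.

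1. *Arm and drug.* The bolus sentence does not name the arm, and names lidocaine only in its second half. It stands after the treatment-group ketamine sentence and before the control-group paragraph, and it refers to the same dose of lidocaine. Lidocaine belongs only to the treatment regimen in the objectives (section 3). Treatment-arm lidocaine is the natural reading.
2. *Awake.* This is inferred. Propofol induces anesthesia in both groups and the section names no sedative before it, although the prophylactic drugs are unspecified. The interval between bolus and propofol is not given.

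The second row of the table is therefore the one study-drug difference between arms that falls before induction.

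**Scale (illustration only)**

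Inputs from the documents: SD 1.9 (section 4.5), 35 per arm (Executive Summary), significance level 0.05 (section 4.12), taken as two-sided because section 4.5 uses 1.96.

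Inputs assumed, because the documents give none: the share p of treatment-arm patients who infer their group, and the mean shift s in their VAS.

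- Standard error of the difference: 1.9 × √(2/35) = 0.454 cm.
- Bias: b = p × s.
- Chance of a significant result favouring the treatment arm at one time point, with no true difference: upper tail of the noncentral t with 68 df and noncentrality b/0.454, beyond the critical value 1.995.

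| p | s (cm) | b (cm) | b/0.454 | Chance if bias favours treatment | Chance if bias has the opposite sign |
|---|---|---|---|---|---|
| – | – | 0 | 0 | 2.5% | 2.5% |
| 10% | 0.5 | 0.05 | 0.11 | 3.2% | 1.9% |
| 30% | 0.5 | 0.15 | 0.33 | 5.1% | 1.1% |
| 50% | 0.5 | 0.25 | 0.55 | 7.8% | 0.6% |
| 30% | 1.0 | 0.30 | 0.66 | 9.5% | 0.5% |
| 50% | 1.0 | 0.50 | 1.10 | 19.1% | 0.1% |

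The results follow wholly from p and s. They show that a modest bias would matter at this sample size, but they do not show that such a bias would occur.

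**The case against.** The best case against the point is that a single bolus is weak evidence of allocation. Patients in both arms have bilateral lines, running fluid, prophylactic drugs, pre-oxygenation and injected induction drugs. Each patient sees only her own sequence, so one more syringe tells her nothing unless she knows the order for each arm. That she was "told about the study process and anesthetic the day before the surgery" does not establish that she does. The documents also describe no sensation from this bolus. All of this stands. It limits the claim to a blind that can break, with unknown frequency.

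Three stronger readings are tempting, and the documents do not support them.

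- *The ketamine infusion also unblinds the awake patient.* Section 4.10 places the infusion after a bolus given during the induction phase. It does not say when the line is connected, or that the patient sees it.
- *The bias must favour the treatment arm.* That requires patients to expect less pain without an opioid. What they are told about the merits of each technique is not in the supplied text, and consent pages were removed before review. A patient who infers that she received no opioid could equally expect more pain.
- *The false-positive rate is inflated to a particular figure.* Every percentage above depends on assumed inputs.

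It may also be said that other features threaten the same outcome more directly. Participants carry the envelope holding their group letter (section 4.7), and section 4.10 trains anesthetists involved in patient management in data collection. Those are separate matters, and resolving them would not supply the missing injection.

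**Conclusion.** The point holds in limited form. As written, one arm receives a study-drug bolus before induction and the other has no matching injection, while the participant is the only blinded party and reports the primary outcome. The difference can reveal allocation, and the plan states no measure to prevent or detect this. The conclusion rests on two readings: that the bolus is treatment-arm lidocaine, which the context supports well, and that before induction means awake, which is likely but not stated.

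The size and direction of any bias cannot be determined from the documents. The range of 3.2% to 19.1% against a nominal 2.5% is conditional on a bias of 0.05 to 0.50 cm towards the treatment arm, and the reverse sign would make a favourable result less likely. The case for acting is that the safeguard is cheap and must be in place before patients are treated. It does not rest on a demonstrated distortion.

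**What to change.** In section 4.10, state that:

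- control patients receive an equal-volume saline injection through the existing IV line at the moment treatment patients receive the pre-induction bolus, with both drawn up in syringes of identical appearance carrying a neutral study-drug label (labelled, because other anesthetic drugs are in use at the same time);
- any arm-specific infusion is set up out of the awake patient's sight;
- each participant's guess of her allocation is recorded at 24 hours, with the last VAS, and reported by arm.

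No study-drug dose or schedule changes. IV access is already in place in both arms and the anesthesia provider already knows the group, so no added staff are needed. The cost is one saline syringe and slight preparation time per control patient, plus one question on the 24-hour form. The recorded guesses will not remove a bias, but they will let readers judge whether the blind held.
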